## 6.4.2 Storage of Study Product

*Sculptra* powder should be stored at controlled room temperature (15-30°C) away from heat. Upon reconstitution, *Sculptra* should be used immediately. Do not freeze.

### 6.4.3 Dispensing and Return

Not applicable, the treatment will be administered by the Treating Investigator at the study center and be documented in the accountability records.

### 6.4.4 Treatment compliance

Not applicable, the treatment will be administered by the Treating Investigator at the study center and be recorded in the eCRF.

### 6.4.1 Case report form recordings

The following should be recorded in the eCRF:

- Date and time of completed injection
- Amount of study product per thigh and session,
- Needle size and number of needles used
- Injection technique used
- Treatment area
- Additional local or topical anesthesia

## 6.5 Randomization

Not applicable, all eligible subjects consenting to participate in the study will receive study product.

### 6.6 Blinding

Not applicable.

CONFIDENTIAL

QMS-9581, CSP template (medical device), version 4.0

Page 36(63)

2021-08-25 16:18

#### 6.7 **Post-trial provisions**

In time, the implant will be degraded in the body and additional treatments will be necessary to maintain the aesthetic result.

#### 7. STUDY ASSESSMENTS AND PROCEDURES

#### 7.1 **Efficacy Assessments**

The methods for collecting effectiveness data are described in this section. To minimize inter-observer variability, every effort should be made to ensure that preferably the same individual who made the initial baseline assessments complete all corresponding follow-up evaluations.

The methods for collecting effectiveness data are:

- Photography
- Time to return to daily activities after treatment will be assessed using subject diaries.
- Global aesthetic improvement by Treating Investigator and Subject using GAIS.

# 7.1.1 Photography

Photographs will be taken in a standardized way to document the condition at baseline, for effectiveness assessments as indicated in Figure 2 Schedule of Assessments, and to document AEs in the treated area. The subject will be standing and wearing a standardized photographic garment.

Camera equipment will be provided by the Sponsor or their designee. Study center personnel designated to take photographs shall be thoroughly trained in the equipment and techniques before study start. The same photographic equipment and standardized setting must be used at each visit (e.g. distance, light, position). Instructions for photography are provided in a separate photography manual.

#### 7.1.2 GAIS

The 7-graded GAIS will be used to assess the aesthetic improvement of cellulite by the Treating Investigator and the subject. The treating Investigator will assess the aesthetic improvement live by comparing to a photograph taken at the baseline visit before the first treatment. The subject will assess the aesthetic improvement by comparing a photograph taken before the first treatment at the baseline visit to a photograph from the current visit. The overall treatment area will be assessed for the right and left posterior thigh separately. The Treating Investigator and the subject will, independently of each other, respond to the question: "How would you describe the aesthetic improvement today compared to the photograph taken before treatment?" by using the respective categorical scale below in Table 2 GAIS.

Doc id

♣ GALDERMA

Title
43CASA2006 CSP Sculptra cellulite

MA-47276

# **Table 2 GAIS**

Rating (Treating Investigator and subject)	Description (only for Treating Investigator)
Very much improved	Optimal aesthetic result for the implant for this subject.
Much improved	Marked improvement in appearance from the initial condition, but not completely optimal for this subject.
Improved	The appearance is improved from the initial condition.
No change	The appearance is essentially the same as baseline.
Worse	The appearance is worse than the initial condition.
Much worse	Marked worsening in appearance from the initial condition.
Very much worse	Obvious worsening in appearance from the initial condition.

Title

43CASA2006 CSP Sculptra cellulite

Doc id

**MA-47276** 

Figure 4CCl

CONFIDENTIAL

Effective date: 2021-06-21 06:13

43CASA2006 CSP Sculptra cellulite

[figure not shown]
Print date: 2021-08-25 16:18

Doc id

MA-47276

♣ GALDERMA

Effective date: 2021-06-21 06:13

CONFIDENTIAL

QMS-9581, CSP template (medical device), version 4.0

[figure not shown]
Page 40(63)

Effective date: 2021-06-21 06:13

Title
43CASA2006 CSP Sculptra cellulite

Doc id

**MA-47276** 

QMS-9581, CSP template (medical device), version 4.0

[figure not shown]
Page 41(63)

Effective

Title
43CASA2006 CSP Sculptra cellulite

Doc id

**MA-47276** 

CONFIDENTIAL

QMS-9581, CSP template (medical device), version 4.0

Page 42(63)

2021-08-25 16:18

# 7.1.5 Volume analysis, surface contour, skin texture/roughness and circumference of the thigh assessments using 3D imaging

Volume analysis (surface relief changes), surface contour, skin texture/roughness and circumference of the thigh will be assessed using **CC** and software. The assessment should be made for each thigh separately. 3D imaging should be performed at baseline, Month 6, Month 9 and Month 12. Camera equipment will be provided by the Sponsor or their designee. Further details regarding the 3D imaging procedure will be specified in a separate user guide. Study centers should follow the maintenance instructions from the equipment manufacturer and keep records of maintenance in the investigator file.

#### 7.1.6 Ultrasound

Dermal thickness will be assessed using ultrasound as indicated in the Schedule of Assessments in Figure 2. The assessment should be made for each thigh separately. Ultrasound equipment will be supplied by the Sponsor or their designee to the study centers. Further instructions regarding the equipment and procedure will be specified in a separate user guide.

#### 7.1.7 Return to daily activities

Time to return to daily activities after treatment will be assessed using subject diaries for 28 days after each treatment.

#### 7.2 **Safety Assessments**

The methods for collecting safety data are described in this section and include:

The methods for collecting safety data are:

- Subject Diary data
- Laboratory assessments
- Device palpability assessment
- Adverse Event reporting
- Device deficiency reporting

## 7.2.1 Subject Diary Data

A subject diary will be dispensed to all subjects for daily completion for 28 days beginning on injection day for each treatment with direct questioning for injection site responses: pain, tenderness, redness, bruising, swelling, itching and other. The presence and maximum intensity (grading for subject diary in Table 3) shall be assessed for the treated area.

Injection site responses that have not been pre-defined in the diary may also be recorded in the diary under "other".

Diary data will be counted and displayed separately from other AE data. All pre-defined diary events ongoing at Day 28, shall be followed up until resolved.

Print date:

2021-08-25 16:18

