### 2.3 Risks and benefits

Risks with Sculptra as with any other injectable implant include infections, perforation of blood vessels, trauma to nerves and lumps. The most common reported adverse events (AEs) after Sculptra treatments are formation of papules and nodules, swelling, mass/induration, of which most resolve with time.

Infection, and damage to body structures such as nerves or blood vessels at the injection site, have also been reported. Rare but serious AEs associated with the intravascular injection of soft tissue fillers in the face have been reported and include temporary or permanent vision impairment, blindness, cerebral ischemia or cerebral hemorrhage, leading to stroke, skin necrosis, and damage to underlying facial structures.

For intravascular complications or embolic events, the treating physician should provide prompt medical attention and follow relevant clinical practice guidelines 15 for handling these symptoms. The treating physician should also review the Intravascular Injection Treatment Protocol  provided separately as a supportive tool.

Lidocaine can, in rare cases, give allergic reactions, and therefore subjects with known allergy or hypersensitivity to local anesthetics should not be included in the study.

The potential risks related to treatment with Sculptra have been assessed and evaluated in accordance with requirements in the ISO 14971 standard and sponsor's established risk management procedures. Based upon the evaluation, risks are considered minimal given the area of injection, depth of injection and volume of product used.

Additional information about reported AEs and anticipated risks are included in the study Instructions for use (IFU) and IB.

Given the anticipated low level of acceptable AEs in connection with the injection, it was determined the risk-benefit assessment for use of Sculptra in this study with the specified reconstitution and injection procedures for improvement in appearance of cellulite appears to offer a clinical benefit at reasonable risk.

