### 4.1 **Overall Design**

### 4.2 Study rationale and justification for design

Aesthetic treatments to correct cellulite have become an increasingly common request and have driven the growing demand for a new, effective and minimally invasive procedure. The desire for smoothening and improving the appearance of dimpled skin has traditionally been met with subcision of fibrous septa, infrared light, laser, radiofrequency, cellulite creams and massage, for example. The use of Sculptra for treatment to improve appearance of cellulite represents a minimally invasive procedure to achieve aesthetic improvement in the posterior thighs.

This study is designed to investigate the feasibility in treatment to improve clinical appearance of cellulite in the posterior thighs using Sculptra. Sculptra stimulates collagen build over time and multiple treatment sessions at least 4 weeks apart is recommended by leading experts . Based on previously performed clinical studies and post-market surveillance data, most AEs occur within two to three weeks of an injection session. In addition to the on-site follow-up visits throughout the study, at which subjects will be questioned by study center personnel about AEs, a subject diary to capture the most common injection-related events for 28 days following each treatment will be utilized in the study to facilitate reporting. The effectiveness peak may be seen up to 12 months after the initial treatment based on previous studies using Sculptra in facial areas. The 12-month duration of the study has been set to ensure the vast majority of AEs and the effectiveness peak is captured within the follow-up period.

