### 6.3.3 Post-treatment care

The injected sites could be gently massaged by the treating Investigator to conform to the contour of the surrounding tissues. Topical cooling may be applied to reduce initial swelling and bruising. After the injection, some common injection-related reactions might occur. These reactions include erythema, swelling, pain, itching, bruising or tenderness at the implant site. Typically, resolution is spontaneous within one week after injection into the skin.

Subjects should be advised not to do vigorous exercise or have vigorous massage within 3 days after injection and to avoid exposing the treated area to heat (sunbathing, ultraviolet-lamp exposure, sauna, steam baths, etc.) until any signs of initial swelling and redness have resolved.

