8.2 Subject Diary Data

A subject diary will be dispensed to all subjects for daily completion for 28 days beginning on injection day for each treatment with direct questioning for injection site responses: pain, tenderness, redness, bruising, swelling, itching and other. The presence and maximum intensity shall be assessed for the treated area:

Table 3. Grading for subject diary data

| Category |
|--------------------------|
| None |
| Tolerable |
| Affects daily activities |
| Disabling |

Number and percentage of subjects reporting each of the pre-defined, expected, posttreatment symptoms listed above, as collected in the 28 days diary, will be presented in total and by maximum intensity for each treatment session. Number of days with the event will be presented for each treatment session by category: 1, 2-7, 8-14, and 15-28 days. A bysubject listing will also be provided.

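### The diary has no prompt for lumps or hardening, which the protocol lists among the most common Sculptra reactions, and the other routes can miss a transient one, above all after session three

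*Protocol*

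**What the plan says.** Protocol section 2.3 names as the most common reported adverse events after Sculptra the "formation of papules and nodules, swelling, mass/induration, of which most resolve with time". Section 4.2 describes "a subject diary to capture the most common injection-related events for 28 days following each treatment".

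Section 7.2.1 sets the direct questions in that diary: "pain, tenderness, redness, bruising, swelling, itching and other". On the last item it adds: "Injection site responses that have not been pre-defined in the diary may also be recorded in the diary under" *other*. It then states "Diary data will be counted and displayed separately from other AE data", and on duration: "All pre-defined diary events ongoing at Day 28, shall be followed up until resolved".

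SAP 8.2 repeats the list of diary items, *other* included, and then plans a table of "Number and percentage of subjects reporting each of the pre-defined, expected, posttreatment symptoms listed above", in total and by maximum intensity for each session, with a by-subject listing. MedDRA coding is stated for adverse events (Protocol 8.6, SAP 8.1). None is stated for diary text.

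**The concern.** The diary is the only instrument that asks about specific local reactions every day. If it does not ask about lumps or hardening, a woman who notices one in the diary window has to volunteer it. Spontaneous mention is usually less complete than a direct question, and least complete for something mild that goes away. Section 2.3 itself says that most of these reactions resolve with time.

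Safety is a stated objective, and section 2.1 says the sponsor intends to use this pilot to initiate a pivotal study if the results are favourable. The frequency and time course of papules, nodules and induration in the thigh are among the things that study would need. An incidence that depends on what women happen to mention, or on what can still be felt at a visit, is a weak basis for it.

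**Working it through.** The documents give no figure on this point, so the check compares texts, plus one calculation of visit gaps.

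**1. Named reactions against prompts**

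| Most common reactions, Protocol 2.3 | Named prompt in 7.2.1 | Place in the diary |
|---|---|---|
| Papules and nodules | No | *other* only |
| Swelling | Yes | own item |
| Mass/induration | No | *other* only |

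Section 6.3.3 has a second list of common reactions: "These reactions include erythema, swelling, pain, itching, bruising or tenderness at the implant site". Taking erythema as redness, it matches all six named prompts. The protocol therefore holds two lists of common reactions, and the diary follows the one without lumps.

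**2. Time between on-site visits**

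Inputs from Figure 2: one month is 4 weeks; sessions two and three each fall one month (+2 weeks) after the session before; Month 6 is ±2 weeks, counted from baseline; the call is 72 ± 24 hours after a session.

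- After sessions one and two, the next on-site visit is 4 to 6 weeks later. The diary covers 28 days, which is 4 weeks.
- Session three falls between week 4 + 4 = 8 and week 6 + 6 = 12.
- Month 6 falls between week 24 − 2 = 22 and week 24 + 2 = 26.
- Gap from session three to Month 6: shortest 22 − 12 = 10 weeks, nominal 24 − 8 = 16 weeks, longest 26 − 8 = 18 weeks.

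Section 4.5.6 words the Month 6 visit as timed from the second treatment. Taken literally, that gives 22 − 6 = 16 to 26 − 4 = 22 weeks. I use the baseline timing, as in Figure 2 and section 4.5.8.

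**3. A lump that appears after the 72-hour call and is gone by the next visit**

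- *Call:* too early, at 2 to 4 days.
- *Palpation (7.2.4):* nothing left to feel. An expected feel would not be an adverse event in any case, and SAP 8.6 only lists palpability. Sections 4.5.4 and 4.5.6 place the check under women who receive treatment at that visit, while Figure 2 marks it for the visit as a whole.
- *Visit question (7.2.5.3):* a general question on health problems since the last visit. After session three it reaches back 10 to 18 weeks.
- *Diary:* an unprompted *other* entry. After session three the diary is collected at Month 6 (section 4.5.8).

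**4. Status of *other***

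- By definition in 7.2.1, *other* is not pre-defined. Sections 7.2.5.3 and 8.6 limit the separate handling to pre-defined, expected events.
- SAP 8.2 points to the symptoms listed above it, and that list ends in *other*. Two programmers could produce different tables from it.
- Follow-up of diary events after Day 28 is stated for pre-defined events only.
- No sentence says who assesses an *other* entry or when it moves to the adverse event form.

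**5. Size**

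The incidence shown would be the true incidence times the fraction captured. The documents give neither.

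**The case against.** The strongest reply is that lumps already have a route. Section 7.2.5.1 counts anticipated events as adverse events, and section 7.2.5.3 requires every adverse event in the eCRF, where it is coded and tabulated by preferred term. Saying that information can come from diaries describes a source; it does not make recording optional. Staff ask about the diary at each 72-hour call and review it when it is collected. Women are asked about adverse events at each visit after screening. An unexpected feel on palpation must be recorded as an adverse event. SAP 8.1 lists related events with onset more than 21 days after treatment, and SAP 8.2 gives a by-subject diary listing. On this view the diary covers general injection reactions (section 6.3.3), and nodule incidence is meant to come from the adverse event table.

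Much of this stands. A reader might infer that the plan hides its main product risk in an uncoded row of expected symptoms. The documents do not support that: the recording rule is mandatory, separate handling is limited to pre-defined events, and SAP 8.2 is ambiguous on *other* rather than explicit.

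What the reply does not answer is ascertainment. A duty to record an event applies only once someone learns of it, and each route can miss a transient lump that nobody asked about. Nor does it reconcile section 4.2, which assigns the most common injection-related events to the diary, with section 2.3. The diary form, IFU and TLF shells are not among the documents and may contain further rules.

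**Conclusion.** The point holds as a gap in ascertainment with an ambiguity in tabulation beside it. Of the three groups of reactions in section 2.3, one has a diary prompt. For the other two, a lump that resolves between visits depends on an unprompted entry or a general question, and the longest interval without an on-site visit after a session is about 10 to 18 weeks, after session three. This rests on the Figure 2 windows, with Month 6 counted from baseline.

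A reader might go on to conclude that the preferred-term table will understate lumps by some stated amount. The documents do not support any such figure; they show only the direction in which incomplete capture would work. The handling of *other* mostly needs clarifying. The missing prompt is the change that would improve the data.

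**What to change.** 1. In Protocol 7.2.1, add one diary prompt, *lumps/bumps/hardening*, graded like the others. Give it its own row in SAP 8.2.
2. In Protocol 7.2.1 and SAP 8.2, state that at diary review the investigator assesses each positive answer to that prompt and each *other* entry and, where it meets the adverse event definition, records it as an adverse event with term, intensity and causality, coded in MedDRA. The assessment step matters, because not every *other* entry will be an adverse event. Events recorded this way then fall under the adverse event rules, including section 7.2.6, and no longer depend on the Day 28 sentence.
3. In SAP 8.2, take *other* out of the table of pre-defined, expected symptoms and list the entries verbatim.
4. Reconcile the lists in sections 2.3 and 6.3.3 with the purpose of the diary in section 4.2.

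The cost is a diary reprint, a few sentences of text and a slightly higher recorded adverse event count. If diaries are already in use, the new row needs its own denominator; items 2 and 3 can still be settled before database lock.

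The prompt works only within the 28-day diary. After session three, 10 − 4 = 6 to 18 − 4 = 14 weeks before Month 6 would still rest on the visit question and palpation. Section 4.2 puts most adverse events within two to three weeks of a session, so the diary window is where the protocol itself expects most of them.

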#### Table 3 Grading for subject diary data

Category	
None	
Tolerable	
Affects daily activities	
Disabling	

#### 7.2.2 Laboratory assessments

For all women of childbearing potential, including those currently using contraception, a urine pregnancy test will be performed at screening, all treatment visits (prior to treatment) and at the final study visit at Month 12. The test result must be negative for the subject to receive any treatment with study product and will be documented in source data and the eCRF.

#### 7.2.3 Pain assessment

Subjects will rate their pain using an **CC** (Appendix 1) where 0 is no pain and 10 is the worst pain imaginable. Pain will be assessed immediately after treatment and 30 minutes after treatment at the initial treatment visit and at all follow-up visits.

## 7.2.4 Device palpability

Device palpability will be assessed at each scheduled visit post-treatment by a qualified staff member and will assess whether the palpability is the normal expected feel. An unexpected feel is to be recorded as an AE.

## 7.2.5 Adverse events

#### 7.2.5.1 Definition of an adverse event (AE) (Medical Devices Regulation (MDR) article 2(57))

An AE is any untoward medical occurrence, unintended disease or injury, or untoward clinical signs (including abnormal laboratory findings) in subjects, users or other persons, in the context of a clinical investigation, whether or not related to the Investigational device.

This definition includes:

- a) events related to the investigational product or the reference product
- b) events related to the procedures involved
- c) events that are anticipated as well as unanticipated

## 7.2.5.2 Definition of a serious adverse event (SAE) (MDR article 2(58))

An SAE is any AE that:

- a) led to death,
- b) led to serious deterioration in the health of the subject, that either resulted in
  - 1. a life-threateningIII illness or injury, or

<sup>1 For users or other persons, this definition is restricted to events related to the investigational product.

GALDERMA
Title
43CASA2006 CSP Sculptra cellulite

MA-47276

- 2. a permanent impairment of a body structure or body function, or
- 3. hospitalisation or prolonged hospitalizationIII, or
- 4. medical or surgical intervention to prevent life-threatening illness or injury or permanent impairment to a body structure or a body function,

Print date:

2021-08-25 16:18

- 5. chronic disease
- c) led to foetal distress, foetal death, or a congenital physical or mental impairment or birth defect

In cases of doubt, whether an AE fulfils a serious criterion or not, there should be a predisposition to report as a SAE rather than not report as such (see Section 7.2.5.5).

